7.4 Assessment of Severity of Adverse Events

The investigator or blinded physician will assess subjects at each visit for the occurrence of AEs. In order to avoid bias in eliciting AEs, subjects should be asked the following non-leading questions: “How are you feeling?” All AEs (serious and non-serious) reported by the subject must be recorded on the CRFs regardless whether a causal relationship to the study drug is suspected.

LYC-30937

Clinical Protocol LYC-30937-2003

Issue Date: 30 August 2016

Severity of AEs will be graded according to National Cancer Institute Common Terminology Criteria for Adverse Events (NCI CTCAE) v4.03.

Adverse events that are not included in the NCI CTCAE lists will be graded according to the NCI CTCAE general guideline for grades as follows:

- Grade 1** Mild, asymptomatic or mild symptoms; clinical or diagnostic observations only; intervention not indicated.
- Grade 2** Moderate, minimal, local intervention, or noninvasive intervention indicated; limiting age-appropriate instrumental activities of daily living (ADL), eg, preparing meals, shopping for groceries or clothes, using the telephone, managing money.
- Grade 3** Severe or medically significant but not immediately life-threatening; hospitalization or prolongation of hospitalization indicated; disabling; limiting self-care ADL, eg, bathing, dressing and undressing, feeding self, using the toilet, taking medications, and not bedridden.
- Grade 4** Life-threatening consequences; urgent intervention indicated.
- Grade 5** Death related to AE

Note the distinction between the severity and the seriousness of an AE. A severe event is not necessarily a serious event. For example, a headache may be severe (interferes significantly with subject's usual function) but would not be classified as serious unless it met one of the criteria for SAEs, listed in Section 7.2.

7.5 Serious Adverse Event Reporting

All observed or volunteered SAEs regardless of treatment group or suspected causal relationship to the study drug will be reported as described below. If an SAE occurs, Lycera or designee is to be notified within 24 hours of awareness of the event by the investigator or designee.

All SAEs and follow-up information must be reported to Lycera or designee within 1 business day or 24 hours of awareness of the event as required by your local requirements by emailing a completed SAE report form to following email address:

SAE Email: **[contact]**

LYC-30937

Clinical Protocol LYC-30937-2003

Issue Date: 30 August 2016

In particular, if the SAE is fatal or life threatening, notification to Lycera or designee must be made immediately, irrespective of the extent of available AE information.

This timeframe also applies to additional new information (follow-up) on previously forwarded SAE reports as well as to the initial and follow-up reporting of exposure in utero (EIU) cases. The investigator should continue to report any significant follow-up information to Lycera or designee up to the point of resolution.

In the rare event that the investigator does not become aware of the occurrence of an SAE immediately (eg, if an outpatient study subject initially seeks treatment elsewhere), the investigator is to report the event within 24 hours after learning of it and document the time of his/her first awareness of the SAE.

The study sponsor medical monitor will perform final medical review of SAEs. Full details of the SAE processing and review procedures will be documented in a safety management plan and medical monitoring plan. Serious adverse events, including any deemed as suspected unexpected serious adverse reactions (SUSAR) will be reported to U.S. FDA within 15 calendar days of notification and within 7 calendar days if the SUSAR is considered life-threatening or resulted in death. A serious adverse reaction is considered "unexpected" if it's not listed in the LYC-30937 IB or is not listed at the specificity or severity that has been observed. Non-SUSAR SAEs will be reported annually as per regulatory guidance.

For all SAEs, the investigator is obligated to pursue and provide information to Lycera or designee in accordance with the timeframes for reporting specified above. In addition, an investigator may be requested by Lycera to obtain specific additional follow-up information in an expedited fashion. In general, the SAE form will include a description/narrative of the event in sufficient detail to allow for a complete medical assessment of the case and independent determination of possible causality. Information on other possible causes of the event, such as concomitant medications and illnesses must be provided. In the case of a subject death, a summary of available autopsy findings must be submitted as soon as possible to Lycera or its designated representative. Expedited safety reports on all unexpected SAEs that are at least possibly related to study procedures will be provided to the FDA.

Subjects with unresolved previously reported SAEs, or new SAEs identified on the last scheduled visit, should be followed by the investigator until the events are satisfactorily resolved. Resolution means the subject has returned to the baseline state of health, the investigator does not expect any further improvement or worsening of the AE, or upon agreement with Lycera or designee.

LYC-30937

Clinical Protocol LYC-30937-2003

Issue Date: 30 August 2016

7.6 Post-Week 14 Reporting of Serious Adverse Events

Any SAEs reported by the subject to the investigator that occur after the last visit and are determined by the investigator to be associated with the use of LYC-30937-EC or with associated study procedures (biopsies), should be reported to Lycera or designee.

7.7 Exposure in Utero

For investigational products within clinical studies, an EIU occurs if:

- A female becomes, or is found to be, pregnant after receiving the study drug (eg, after Study Day 1).

If any study subject becomes pregnant during their participation in the study, the subject will stop study drug and withdraw from the study. The investigator must submit this information to Lycera or designee on the EIU Form. This must be done irrespective of whether an AE has occurred and within 24 hours of awareness of the pregnancy. The information submitted should include the anticipated date of delivery (see below for information related to an induced termination of pregnancy).

Follow-up is conducted to obtain pregnancy outcome information on all EIU reports with an unknown outcome. The investigator will follow the pregnancy until completion or until pregnancy termination (ie, induced abortion) and then notify Lycera or designee of the outcome. The investigator will provide this information as a follow up to the initial EIU Form. The reasons(s) for an induced abortion should be specified. An EIU report is not created when an ectopic pregnancy report is received since this pregnancy is not usually viable, however such events should be considered as SAEs and the investigator should follow the procedures for reporting SAEs.

If the pregnancy outcome meets the criteria for immediate classification as an SAE (ie, spontaneous abortion, stillbirth, neonatal death, or congenital anomaly [including resulting in an aborted fetus, stillbirth or neonatal death]), the investigator should follow the procedures for reporting SAEs.

In the case of a live birth, the “normality” of the newborn can be assessed at the time of birth (ie, no minimum follow-up period of a presumably normal infant is required before an EIU Form can be completed). The “normality” of an aborted fetus can be assessed by gross visual inspection, unless pre-abortion test findings are suggestive of a congenital anomaly.

LYC-30937

Clinical Protocol LYC-30937-2003

Issue Date: 30 August 2016

Additional information about pregnancy outcomes that are classified as SAEs follows:

- “Spontaneous abortion” includes miscarriage and missed abortion.
- All neonatal deaths that occur within 1 month of birth should be reported, without regards to causality as SAEs. In addition, any infant death after 1 month that the investigator assesses as possibly related to the in utero exposure to the investigational medication should be reported.

7.8 Relationship/Causality of Adverse Events/Serious Adverse Events

The investigator’s assessment of causality must be provided for all AEs (serious and non-serious). The causality assessment is the determination of whether there exists a reasonable possibility that the study drug itself (eg, LYC-30937-EC or placebo) caused or contributed to an AE.

If the final determination of causality is unknown and the investigator does not know whether the study drug caused the event, then the event will be handled as “related to study drug” for reporting purposes. If the investigator’s causality assessment is “unknown, but not related to study drug”, this should be clearly documented on study records and will be categorized as “not related to study drug” for reporting purposes.

Relationship of an AE to the study drug will be assessed as follows:

Unrelated [Not Related or Unlikely Related]: There is not a temporal or causal relationship to the study drug. If the AE is “unrelated” to the study drug, the investigator must assess whether the event is thought to be related to the disease under study, concomitant medication, other illness, other, or unknown.

Related [Definite]: There is reason to conclude that the study drug caused the AE.

Suspected [Possible or Probable]: There is evidence to suggest a causal relationship between the study drug and the AE. For analysis purposes, “Suspected [Possible or Probable]” events are categorized as “Related.”

7.9 Withdrawal Due to Adverse Events

Withdrawal due to AEs must be recorded on the appropriate AE CRF page.

LYC-30937

Clinical Protocol LYC-30937-2003

Issue Date: 30 August 2016

When a subject withdraws due to an SAE, the SAE must be reported in accordance with the reporting requirements as defined.

7.11 Study Hold or Stopping Criteria

The sponsor has the right to terminate the study prematurely for safety or administrative reasons. In all cases, necessary measures will be taken to ensure appropriate safety follow-up of all subjects in the trial.

Individual subjects may interrupt or stop study drug at the discretion of the investigator or medical monitor any time for safety reasons. Individual subjects must discontinue if they experience a study drug-related grade 3 (CTCAE) severity AE of special interest – see Section 6.4.6 for list of AEs of special interest.

ECGs are scheduled to be performed at Week 12 (end of treatment). An additional ECG should be performed if a subject reports symptoms of recurrent palpitations, recurrent, persistent lightheadedness or faintness, or any symptom that the investigator deems for cause. Subjects should report these symptoms to the investigator immediately and return to the clinic as soon as possible for evaluation including an ECG. Subjects will discontinue study drug if marked QT/QTc prolongation of > 500 ms or > 60 ms over baseline is present.

7.11.1 Suspension of Study

The study will be suspended if any subject experiences a drug-related adverse event that meets grade 4 or 5 CTCAE severity criteria or if 2 or more subjects experience the same type of grade

LYC-30937

Clinical Protocol LYC-30937-2003

Issue Date: 30 August 2016

2 study drug-related adverse event and/or meets the serious criteria as defined in Section 7.2. The unblinded medical reviewer will review these cases to determine treatment assignment. Adverse event reports will be submitted to regulatory agencies and clearance received before any further dosing takes place.

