9.4 Study Termination

Premature termination of this study or part of the study may occur because of a regulatory authority decision, change in opinion of the IRB/IEC, safety problems, or at the discretion of Lycera. In addition, Lycera retains the right to discontinue development of LYC-30937-EC at any time.

If a study is prematurely terminated or discontinued, Lycera will promptly notify the investigator. After notification, the investigator must notify all subjects currently participating in the study within a specific timeframe designated by Lycera. As directed by Lycera, study materials will be collected and all CRFs completed to the greatest extent possible.

LYC-30937

Clinical Protocol LYC-30937-2003

Issue Date: 30 August 2016

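### Read literally, the study-suspension rule is triggered by two same-type grade 2 events but not by two same-type non-serious grade 3 events

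*Protocol*

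**What the plan says.** Protocol Section 7.11.1 has two limbs. The first suspends the study if any subject has a drug-related event of CTCAE grade 4 or 5. The second applies "or if 2 or more subjects experience the same type of grade" "2 study drug-related adverse event and/or meets the serious criteria as defined in Section 7.2". These two fragments are consecutive words of one sentence that crosses a page boundary.

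A trigger has fixed consequences. An unblinded medical reviewer determines treatment assignment, and "Adverse event reports will be submitted to regulatory agencies and clearance received before any further dosing takes place".

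Four other provisions bear on the point:

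- Section 7.11 has a grade 3 rule for the individual: "Individual subjects must discontinue if they experience a study drug-related grade 3 (CTCAE) severity AE of special interest".
- Section 7.4 separates severity from seriousness: "A severe event is not necessarily a serious event".
- Section 7.11 gives a discretionary power: "The sponsor has the right to terminate the study prematurely for safety or administrative reasons". Section 9.4 is similar: "Premature termination of this study or part of the study may occur because of a regulatory authority decision", among other grounds.
- Section 7.8 asks whether "the study drug itself (eg, LYC-30937-EC or placebo) caused or contributed to an AE", so an event can be judged drug-related in either arm while the study is blinded.

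The SAP contains no suspension rule.

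**The concern.** A safety trigger should be monotone in severity: if a cluster of moderate events stops dosing, a cluster of severe ones should too. Section 7.11.1 does not have this property as printed. It covers grade 4 or 5 in one subject and grade 2 in two subjects, and says nothing of grade 3.

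What is at stake is the mandatory sequence of suspension, unblinded review and regulatory clearance. Stopping individual subjects does not start that sequence, and a right to terminate does not oblige anyone to use it. The rule has to be applied the same way across about six sites (Section 4.2), in the first efficacy study in this population (Section 2.6). Dosing lasts 12 weeks, against 7 days of earlier repeat dosing (Section 2.4).

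A secondary problem is the serious clause, which is loosely attached. It can be read in parallel with the first limb, so that one drug-related serious event suffices, or as a further description of the same-type pair. The sentence does not settle which.

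**Working it through.** **The rule as text.** Take two subjects with the same type of non-serious, drug-related event.

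| Worst grades in the two subjects | As printed | With grade 2 or higher |
|---|---|---|
| 2 and 2 | suspend | suspend |
| 2 and 3 | no mandatory suspension | suspend |
| 3 and 3 | no mandatory suspension | suspend |
| either is 4 or 5 | suspend | suspend |

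**Whether another provision fills the gap.** The grade 3 rule in Section 7.11 stops the individual subject, and only for drug-related events of special interest. The withholding rules in Section 6.4.6 are also subject-level. The powers in Sections 7.11 and 9.4 are discretionary. Section 7.10 (Medical Monitoring) is not in the text available and is not relied on.

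**Size, as illustration.** The protocol states no operating characteristic for this rule, so there is no figure to reproduce. Inputs:

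- n = 30 randomized subjects (Section 8.1). Both arms count because causality is judged for drug or placebo (Section 7.8).
- p2 = per-subject probability of a drug-related grade 2 event of one type; p3 = the same for a non-serious drug-related grade 3 event. Both are assumed: p2 at 1, 2 and 5%; p3 at 0.25, 0.5 and 1%.
- Each subject is counted once, at worst grade.

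Formula: T(p) = P(Bin(30, p) ≥ 2) = 1 − (1 − p)^30 − 30p(1 − p)^29. The printed rule triggers with probability T(p2), the corrected rule with T(p2 + p3). The difference is the chance of a cluster that the printed rule misses.

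Worked case, p2 = 2%, p3 = 1%:

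- T(0.02) = 1 − 0.5455 − 0.3340 = 0.1205
- T(0.03) = 1 − 0.4010 − 0.3721 = 0.2269
- Missed: 0.1064

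Of this, exactly one grade 2 plus one grade 3 contributes 30 × 29 × 0.02 × 0.01 × 0.97^28 = 0.0742. Two or more grade 3 with at most one grade 2 contributes the remaining 0.0322.

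| p2 | T(p2) | Missed, p3 = 0.25% | Missed, p3 = 0.5% | Missed, p3 = 1% |
|---|---|---|---|---|
| 1% | 0.0361 | 0.0178 | 0.0381 | 0.0844 |
| 2% | 0.1205 | 0.0253 | 0.0517 | 0.1064 |
| 5% | 0.4465 | 0.0255 | 0.0504 | 0.0981 |

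Differences are taken before rounding. If related events arose only in the 20 subjects on active drug, the same formula with n = 20 gives, at 2% and 1%, 0.1198 − 0.0599 = 0.0599.

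**Several event types.** For four independent types at the same rates, use 1 − (1 − T)^4. The smallest rise is 0.906 to 0.922, or 0.016 (5%, 0.25%). The largest is 0.137 to 0.402, or 0.265 (1%, 1%).

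**Serious clause.** The chance of at least one related serious event in 30 subjects is 1 − (1 − p)^30: 0.072, 0.140 and 0.260 at an assumed 0.25, 0.5 and 1% per subject.

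**The case against.** The strongest reply is that nobody would apply the rule literally. A stated grade in a safety trigger is naturally taken as a floor, and a sensible medical monitor would suspend for two grade 3 events. That is very probably the intent, and it limits the practical harm. It also supports the edit, because a mandatory rule should not rely on readers supplying the missing words.

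Other points narrow the finding without removing it:

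- **Overlap with serious.** The grade 3 definition in Section 7.4 includes hospitalization indicated and disabling, so many grade 3 events would also be serious under Section 7.2. The uncovered category is therefore smaller than all grade 3 events, but Section 7.4 says it exists.
- **Wrong number.** The text may be a slip for grade 3, in which case a grade 2 minimum would fix an oversensitive trigger in place. At 5% and 1% the corrected rule suspends with probability 0.54 for one event type and 0.96 over four; a grade 3 pair rule at 1% triggers with probability 0.036. Nothing in the documents shows such a slip, and the recommendation keeps the printed grade.
- **Lost symbol.** The page boundary falls between the word grade and the numeral, so a lost sign cannot be fully excluded. Such signs survive elsewhere in the text.
- **Assumed rates.** With p2 = 0.5% and p3 = 0.1% the gap is only 0.4 points. All 52 treatment-emergent events in Phase 1a were mild, one possibly related event occurred on active drug, and Phase 1b reported no adverse events (Section 2.4). Exposure there was short, so higher rates are not excluded.
- **Counting at worst grade.** A subject whose event passes through grade 2 to grade 3 has arguably experienced grade 2 and would count under the printed rule. The missed probabilities are then overstated.

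**Conclusion.** The point holds on the printed text. The paired trigger is out of severity order: it mandates suspension for same-type grade 2 pairs and omits non-serious grade 3 pairs and mixed grade 2 and 3 pairs. No other mandatory study-level trigger in the available text covers those cases. That conclusion rests on wording alone.

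The range of 1.8 to 10.6 percentage points for one event type is a rough illustration. It assumes n = 30, independent subjects, worst-grade counting and event rates that the documents do not supply. This should be fixed: it is a drafting gap in a mandatory safety rule, partly mitigated by subject-level stops and discretionary powers, and cheap to close. The ambiguity of the serious clause is secondary.

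**What to change.** Make the paired grade a minimum. Suggested wording: *or if 2 or more subjects experience the same type of study drug-related adverse event of grade 2 or higher*.

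As a clarification, give the serious clause its own subject: *or if any subject experiences a study drug-related adverse event that meets the serious criteria in Section 7.2*. If only same-type pairs were meant, say that instead.

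The main edit needs no new data, visits or analyses. If a minimum was always intended, it adds no suspensions. Against the literal reading, its cost equals the missed probability above, for example from 12.1% to 22.7% at 2% and 1%, or about 2 to 27 points over four event types. Each added suspension brings unblinded review and a halt until clearance, and each involves at least one drug-related grade 3 event.

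The single-event serious wording costs nothing if that reading was intended. If pairs were meant, it adds at most the 7% to 26% shown above.

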8.0 STATISTICAL AND ANALYTICAL PLAN

8.1 Sample Size Calculation

A total of approximately 30 subjects will be randomized into the study and using a 2:1 randomization ratio of LYC-30937-EC 25 mg or placebo daily.

A sample size of 30 subjects (20 LYC-30937-EC and 10 placebo) will achieve approximately an 80% power to detect difference in the mean percent change from baseline in PASI at Week 12 in the LYC-30937 treatment group compared to the placebo treatment group. The mean percent change from baseline in PASI at Week 12 in the placebo treatment group is assumed to be 16.7% with SD=32.0.^[16] The power was computed assuming the mean percent change from baseline in PASI at Week 12 in the LYC-30937-EC treatment group is at least 52.7% (SD=32.0) for a mean difference of at least 36.0%. The test statistic used is the two-sided t-test. The alpha level of the test was targeted at 0.05.

8.2 Analysis Populations

8.2.1 Full Analysis Set

The full analysis set (FAS) is defined as all randomized subjects. Subjects will be included in the treatment group to which they were randomized, regardless of the treatment they actually received. All efficacy analyses will be performed on the FAS.

8.2.2 Safety Set

The safety set is defined as all randomized subjects who received at least one dose of study drug. For summaries/listings where treatment group is included, subjects will be included in the treatment group to which they were actually treated. All safety analyses will be performed on the Safety Set.

LYC-30937

Clinical Protocol LYC-30937-2003

Issue Date: 30 August 2016

8.3 Demographic and Subject Characteristics

Demographic information and subject characteristics such as gender, race, age, and baseline vital signs, baseline PASI score, baseline % total BSA involvement, and baseline static IGA will be summarized by treatment group and overall.

8.4 General Statistical Considerations

For safety and efficacy endpoints, baseline will be defined as the last observation prior to dosing.

Continuous safety and efficacy endpoints will be summarized using mean, standard deviation, median, minimum, and maximum. Discrete safety and efficacy endpoints will be summarized by the number and percent of subjects in each category. Continuous efficacy endpoints will be analyzed using an analysis of covariance model with treatment as a factor and baseline value as a covariate. Discrete variables will be analyzed using a chi-square test. There will be no adjustments for multiplicity. Additional details of the statistical analyses will be described in the statistical analysis plan (SAP).

